### **Sub-Study Objectives**

1. To characterize systemic amikacin exposure, including approximate systemic bioavailability in Japanese subjects, using a population PK model to describe the disposition of amikacin in the serum
2. To compare population PK modeling between Japanese subjects to historical population PK modeling for LAI
3. To evaluate the amikacin concentration in sputum

### **Sub-Study Design**

At Baseline (Day 1), Japanese subjects at Japanese sites who are randomized to the LAI plus multi-drug regimen arm and signed the Comprehensive PK Sub-Study informed consent will be able to participate. PK blood and sputum samples will be collected from PK subjects at Baseline (Day 1) and at Months 1, 3, and 6. Details on sample collection timepoints are listed in the Sub-Study Procedure section below. The Comprehensive PK Sub-Study will enroll subjects until 8 subjects complete all required assessments and have evaluable data. .

### **Sub-Study Endpoints**

1. Characterize systemic amikacin exposure, including approximate systemic bioavailability in Japanese subjects
2. Compare Japanese subjects to historical population using PK modeling
3. Evaluate the amikacin concentration in sputum

### **Sub-Study Population**

Protocol Amendment #3 version: 22 February 2016

*This protocol is solely for the purpose of communicating information about the investigational drug between Insméd Incorporated and study personnel. Information is not to be reproduced, abstracted or used for sharing of information for any other purpose, whatsoever, except with the written permission of Insméd Incorporated.*

Only Japanese sites will participate in this sub-study once they have IRB/EC approval for the main INS-212 study and for this sub-study. All subjects must meet eligibility criteria for the main INS-212 study, must give written informed consent for that study, and must also give written informed consent for this sub-study. Eight evaluable subjects are expected to participate in the Comprehensive PK sub-study. There are no separate inclusion or exclusion criteria for this sub-study besides the requirement for written informed consent.

### **Sub-Study Procedures**

Either at Screening or at Baseline (Day 1), subjects will be asked to provide informed consent for this sub-study. Blood and sputum samples will be collected to determine amikacin concentrations. The Schedule of Events for the Comprehensive PK Sub-Study is provided in [Table 14-2](#).

#### *PK sputum sample collection timepoints*

On Day 1, two to three (2-3) sputum samples will be collected at the following timepoints: 0 to 1 hour prior to study drug administration and at 8 (optional) and 24 hours after study drug administration. At Months 1, 3, and 6, PK sputum will be collected 0 to 1 hour prior to study drug administration and 1 to 4 hours after study drug administration. Day 1 and Month 3 PK sputum samples must be collected in conjunction with the 8 PK blood draws on the same day and time (within 30 minutes of blood being collected) as indicated below.

#### *PK blood sample collection timepoints*

On Day 1 and at Month 3, subjects will have 8 PK blood sample collections at the following timepoints: 0 to 1 hour prior to study drug administration, and at 1, 2, 4, 6, 8, 12, and 24 hours after study drug administration ( $\pm 5$  minutes at each time point is allowed). At Months 1 and 6, PK blood samples will be collected 0 to 1 hour prior to study drug administration and 1 to 4 hours after study drug administration.

Protocol Amendment #3 version: 22 February 2016

*This protocol is solely for the purpose of communicating information about the investigational drug between Insmmed Incorporated and study personnel. Information is not to be reproduced, abstracted or used for sharing of information for any other purpose, whatsoever, except with the written permission of Insmmed Incorporated.*

All samples will be stored at or below  $-20^{\circ}\text{C}$  before shipping to a central PK laboratory. Details for collecting, handling, storing, and transporting blood and sputum samples for PK analyses will be provided in the site laboratory manual.

**Table 14-2 Schedule of Events for INS-212 Comprehensive Pharmacokinetic Sub-Study**

INS-212 Comprehensive Pharmacokinetic Sub-Study				
	Baseline	Month 1	Month 3	Month 6
	(V2)	(V3)	(V5)	(V8)
Visit Window	Day 1	(±3 days)	(±3 days)	(±3 days)
Informed Consent a	X	–	–	–
PK Blood Sampling b	pre-dose: 0-1 hr	pre-dose: 0-1 hr	pre-dose: 0-1 hr	pre-dose: 0-1 hr
	post dose: 1, 2, 4, 6, 8, 12, 24 hrs	post dose: 1-4 hrs	post dose: 1, 2, 4, 6, 8, 12, 24 hrs	post dose: 1-4 hrs
PK Sputum Sampling	pre-dose: 0-1 hr	pre-dose: 0-1 hr	pre-dose: 0-1 hr	pre-dose: 0-1 hr
	post dose: 8 (optional), 24 hrs	post dose: 1-4 hrs	post dose: 1-4 hrs	post dose: 1-4 hrs
Administer Study Drug at Site	X	X	X	X

a The subject will be asked to provide informed consent for this sub-study at either Screening or at Baseline (Day 1). Informed consent must be obtained prior to any procedures for this sub-study can be performed.

b blood samples have a window of ( $\pm 5$  minutes at each time point)

Protocol Amendment #3 version: 22 February 2016

*This protocol is solely for the purpose of communicating information about the investigational drug between Insmad Incorporated and study personnel. Information is not to be reproduced, abstracted or used for sharing of information for any other purpose, whatsoever, except with the written permission of Insmad Incorporated.*

Confidential

## **Introduction**

LAI is a novel formulation of amikacin that is encapsulated in liposomes comprised of DPPC and cholesterol (naturally occurring lipids in the lung) to allow for effective delivery in the lung, leading to high concentrations of the drug at the target sites of infection, with low systemic levels. In clinical study TR02-112 LAI in addition to standard background therapy was statistically superior at the end of the double-blind period (Day 84) for achieving a negative sputum culture compared to those who received placebo in addition to standard background therapy.

Study INS-212 will evaluate whether there are any radiographical changes that occur in subjects who have achieved culture conversion and continued on treatment.

## **Sub-Study Objective**

1. To compare assessments of radiographs, read by a trained medical professional, from Baseline (Day 1) in CT scans at EOT in a subset of subjects within each treatment arm

## **Sub-Study Design**

Eligible subjects must be enrolled into the INS-212 study. At randomization (Day 1), any subject who has signed the informed consent for this chest CT Scan Sub-Study will participate; there is no maximum number of subjects that can participate. At the latest, the informed consent and the subject's Baseline chest CT scan must be collected no later than 2 weeks after the subject's first dose of LAI or multi-drug regimen in the INS-212 study. A prior chest CT scan may be used as a subject's Baseline measure if this CT scan was obtained within 6 months from the subjects Day 1 study visit. All subjects in this chest CT Scan Sub-Study will have their follow-up chest CT scan on the (EOT) visit ( $\pm 14$  days) provided the last chest CT scan was not obtained within the prior 6 months. High resolution CT scan is preferred, if available.

## **Sub-Study Endpoint**

Protocol Amendment #3 version: 22 February 2016

*This protocol is solely for the purpose of communicating information about the investigational drug between Insmad Incorporated and study personnel. Information is not to be reproduced, abstracted or used for sharing of information for any other purpose, whatsoever, except with the written permission of Insmad Incorporated.*

1. Radiological changes in CT scan, within a sub-set of subjects, at EOT in the LAI arm compared to multi-drug regimen alone, where appropriate

### **Sub-Study Population**

Only sites that have agreed to and have the ability to perform the chest CT scans will participate in this sub-study once they have IRB/EC approval for the main INS-212 and for this chest CT Sub-Study. Subjects must provide written informed consent for both the main INS-212 study and for this sub-study. It is expected that at least 60 subjects will participate in this CT Scan Sub-Study.

### **Sub-Study Procedures**

On Day 1 ( $\pm 14$  days) subjects will be asked to provide informed consent for this sub-study. Once the informed consent has been signed the subject should have a chest CT scan performed (a prior CT scan that was obtained within 6 months prior to signing the informed consent may be used for Baseline). A CT scan should not be performed during Screening for this CT-Scan Sub-Study. It will be performed at Baseline (Day 1) once the subject is randomized. A second chest CT scan will be performed when a subject has completed treatment (EOT  $\pm 14$  days), which includes any subject that prematurely discontinues study drug provided that more than 6 months have elapsed since their last CT scan. High resolution CT scan is preferred, if available.

All chest CT scans will be read locally and a description of findings for each scan will be entered into the eCRF page. An overall assessment of improved, worsening, or no change from previous scan will be reported for all scans after the subject's Baseline scan. All chest CT scans must be made available to the Sponsor to be stored as study source documentation.

Protocol Amendment #3 version: 22 February 2016

*This protocol is solely for the purpose of communicating information about the investigational drug between Insmmed Incorporated and study personnel. Information is not to be reproduced, abstracted or used for sharing of information for any other purpose, whatsoever, except with the written permission of Insmmed Incorporated.*

**Table 14-3 Schedule of Events for INS-212 CT Scan Sub-Study**

INS-212 CT Scan Sub-Study		
	Baseline	EOT
	(V2)	
Visit Window	(-6 months to +14 Days)	(±14 days)
Informed Consent a	X	–
CT Scan of Chest	X	X
a informed consent for this sub-study must take place after the subject has been enrolled and randomized into the INS-212 study. This will be a separate informed consent from the INS-212 main study. b Computed tomography of the chest at Baseline (Day 1) is performed only for those subjects whom have signed the CT Scan Sub-Study informed consent if not completed within 6 months before the first dose of LAI or multi-drug regimen at the Baseline (Day 1) visit. EOT scan is required if no less than 6 months have elapsed since the previous CT scan was performed.		

Protocol Amendment #3 version: 22 February 2016

*This protocol is solely for the purpose of communicating information about the investigational drug between Insmmed Incorporated and study personnel. Information is not to be reproduced, abstracted or used for sharing of information for any other purpose, whatsoever, except with the written permission of Insmmed Incorporated.*

Confidential

APPENDIX 5

JAPAN SPECIFIC CT SCAN SUB-STUDY

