## **9.3 RANDOMIZATION AND BLINDING**

Eligible subjects will be randomized 2:1 to open-label treatment with LAI plus a multi-drug regimen or a multi-drug regimen alone.

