### **9.6.3 Exploratory Endpoint Analyses**

The change in 6MWT distance at Month 6 for converters compared with non-converters overall for ITT population, within LAI plus a multi-drug regimen, within the multi-drug regimen alone, the change in BMI at Month 6 for LAI plus a multi-drug regimen compared with a multi-drug regimen alone, and the changes in chest CT scan at EOT for LAI plus a multi-drug regimen compared with a multi-drug regimen alone in a sub-set of subjects will be analyzed using the ANCOVA models with the comparison arm (converters vs. non-converters or the treatment arm) and the randomization strata as factors, and the corresponding Baseline measure as a covariate. If a CT scan is not performed at EOT for any subject, then prior CT scan will be used in the analysis.

The change from Baseline (Day 1) to Month 6 and EOT in the EQ-5D-3L patient reported health outcomes will be analyzed for the ITT population similarly using the same MMRM method as the analysis of the change from Baseline to EOT in 6MWT distance. Kaplan-Meier estimates for the distribution of time to death will be constructed by treatment arm. The treatment comparison will be made using the stratified log rank test for the ITT population. Incidence of new MAC strains will be summarized by treatment arms.

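### Appendix 4 CT sub-study: optional consent is taken after open-label randomisation, so entry can depend on the known arm and the exploratory between-arm CT comparison is open to selection

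*Protocol*

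**What the plan says.** Appendix 4 deals with the timing of sub-study consent in three places.

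- Table 14-3, footnote a, is mandatory: "informed consent for this sub-study must take place after the subject has been enrolled and randomized into the INS-212 study". The same footnote makes this consent separate from the main-study consent.
- Sub-Study Design: "At randomization (Day 1), any subject who has signed the informed consent for this chest CT Scan Sub-Study will participate". The next sentence sets an outer limit for both the consent and the baseline scan, which "must be collected no later than 2 weeks after the subject's first dose of LAI or multi-drug regimen".
- Sub-Study Procedures: on Day 1, with a window of 14 days either side, "subjects will be asked to provide informed consent for this sub-study". No scan is to be made for the sub-study during Screening: "It will be performed at Baseline (Day 1) once the subject is randomized".

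The main trial is not blinded. Section 5.6 (Blinding) reads simply None, and Section 9.3 says "Eligible subjects will be randomized 2:1 to open-label treatment with LAI plus a multi-drug regimen or a multi-drug regimen alone".

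The sub-study endpoint in Appendix 4 is a between-arm contrast: "Radiological changes in CT scan, within a sub-set of subjects, at EOT in the LAI arm compared to multi-drug regimen alone, where appropriate". It is exploratory endpoint 10 in Section 3.4. Section 9.6.3 analyses "the changes in chest CT scan at EOT for LAI plus a multi-drug regimen compared with a multi-drug regimen alone in a sub-set of subjects" by ANCOVA, with arm and randomisation strata as factors and the corresponding baseline measure as covariate.

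**The concern.** Randomisation makes the arms comparable among everyone randomised. A subset keeps that property if membership is settled before allocation, or without regard to it. Here membership is voluntary and is decided after an allocation that subject and staff both know. Up to two weeks of treatment may also have passed, and early experience is likely to differ by arm: Section 5.3 describes local respiratory events on LAI that became less frequent with continued use.

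If willingness to join is related to prognosis in one arm and not in the other, or in opposite directions, the two CT groups differ before any treatment effect. Adjusting for strata and baseline CT deals with selection that acts through those measures. It does not deal with selection through anything unmeasured. What is at stake is how the exploratory CT result may be read: as a randomised comparison, or as an observational one within a trial.

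**Working it through.** **1. Consent timing, side by side**

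| Place in Appendix 4 | Consent before randomisation? | Consent after the arm is known? |
|---|---|---|
| Sub-Study Design | Can be read as already signed at randomisation, but not required | Allowed, to 2 weeks after first dose |
| Sub-Study Procedures | Window nominally reaches back before Day 1 | Allowed, to 14 days after Day 1 |
| Table 14-3, footnote a | Not allowed | Required |

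On every reading, consent after the arm is known is at least allowed. The only mandatory rule on order requires it. The places also conflict: a site that obtains consent before Day 1, inside the Sub-Study Procedures window, breaches footnote a.

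**2. Is the order needed to avoid scanning screen failures?** No. Sub-Study Procedures already prevents that by barring scans during Screening and placing the scan after randomisation. Consent can move without moving a scan. The Comprehensive PK sub-study (Appendix 3) already permits its consent at Screening.

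**3. Scale of the sub-study.** At least 60 subjects are expected (Appendix 4, Sub-Study Population), against up to about 351 randomised and 261 evaluable (Section 3.6.1). 60/351 = 17% and 60/261 = 23%. At 2:1, 60 subjects split 40:20. The 17% is a share of the whole trial, not uptake among those invited, because only agreeing and capable sites take part. The sub-study has no power statement to reproduce.

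**4. Illustration on assumed inputs.** None of these inputs comes from the protocol. There is no true treatment effect, with 40 LAI and 20 control subjects. The outcome has SD 1 and correlation ρ with an unmeasured prognostic factor U (SD 1). About 17% consent. In the LAI arm the odds of consent are multiplied by OR per SD of U; in control, consent is unrelated to U. Each setting is a two-sample t-test over 6,000 simulated sub-studies. U stands for whatever strata and baseline CT leave unexplained.

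Expected spurious difference = ρ × mean of U among consenting LAI subjects.

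| ρ | OR | Mean U, LAI consenters | ρ × mean U | Simulated difference (SD) | Rejections at nominal 5% |
|---|---|---|---|---|---|
| 0.3 | 1.0 | -0.007 | -0.002 | -0.001 | 5.2% |
| 0.3 | 1.5 | 0.330 | 0.099 | 0.098 | 6.9% |
| 0.3 | 2.0 | 0.525 | 0.158 | 0.155 | 8.2% |
| 0.5 | 1.0 | -0.003 | -0.002 | -0.001 | 4.8% |
| 0.5 | 1.5 | 0.326 | 0.163 | 0.171 | 9.1% |
| 0.5 | 2.0 | 0.526 | 0.263 | 0.262 | 16.1% |

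Check on scale: the standard error of the difference is √(1/40 + 1/20) = 0.274. The largest shift is 0.263/0.274 = 0.96 of a standard error and the smallest non-null one is 0.099/0.274 = 0.36. When consent is unrelated to prognosis, the error stays near 5%.

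**The case against.** **Low stakes.** The endpoint is exploratory, confined to a subset, qualified as applying where appropriate, and carries no power claim. This stands. Nothing here touches the primary or secondary analyses.

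**Bias is possible, not shown.** It arises only if consent depends on prognosis differently in the two arms, and the protocol holds no evidence that it does. This stands too. A reader might infer that the CT comparison has lost its randomised basis altogether. The text supports only that the design leaves it open to selection. Nor would unequal uptake by itself show bias: a lopsided split costs precision, and bias needs selection on prognosis as well.

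**Sites do not choose by arm.** A reader might take the rule to mean that sites opt in or out knowing the allocation. They do not: Sub-Study Population settles site participation by agreement, capability and IRB/EC approval. What remains is that staff at a participating site can invite individual subjects knowing their arm.

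**Other weaknesses would remain.** Non-converters and subjects who relapse leave at Month 8, while converters reach EOT as late as Month 16, so the EOT scan falls at different times according to response. Scans are read locally and no blinding of the reader is stated. This is correct. Earlier consent removes one source of selection and does not by itself secure the comparison.

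**It is only an inconsistency.** The three places do disagree, and that is the firmest part of the point. Reconciling them in favour of footnote a, however, would make consent after allocation universal, so the direction of the correction matters.

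**Conclusion.** The point holds for the Appendix 4 sub-study as a minor design weakness with a cheap remedy. Optional consent is required after open-label allocation by one rule and allowed up to 14 days after first dose or Day 1 by the other two. No other section prevents entry from depending on the arm or on early tolerability. The planned adjustment does not cover selection on unmeasured factors.

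The size cannot be derived from the protocol. The range of 0.10 to 0.26 SD, with error of 7% to 16%, rests wholly on the assumed odds ratios of 1.5 to 2.0, correlations of 0.3 to 0.5, and selection in one arm only. It shows what moderate selection could do in a sub-study of this size, not what is expected.

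The conclusion should not be carried to the Japan CT sub-study in Appendix 5. There, consent is part of the main-study consent at Screening and all Japanese subjects at sites in Japan take part. For the same reason Table 14-4 is only a loose precedent: it contains no optional consent to time. The SAP is not at hand and might label the CT comparison as non-randomised, but the timing of consent is fixed in the protocol.

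**What to change.** Reword footnote a of Table 14-3, Sub-Study Design and Sub-Study Procedures together, so that all three say sub-study consent is obtained before randomisation, at Screening or on Day 1 before allocation. All three must change: correcting only footnote a would leave the other two allowing late consent. The timing of the scan stays as it is.

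For subjects already entered under the present wording, describe the between-arm CT comparison as non-randomised. Report, by arm, how many joined and their baseline characteristics, beside those of subjects who did not join.

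The cost is wording, plus some consents taken from subjects who then fail screening. The change does not address the differing EOT times of converters and non-converters, or local reading without stated reader blinding.

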**Introduction**

Protocol Amendment #3 version: 22 February 2016

*This protocol is solely for the purpose of communicating information about the investigational drug between Insmmed Incorporated and study personnel. Information is not to be reproduced, abstracted or used for sharing of information for any other purpose, whatsoever, except with the written permission of Insmmed Incorporated.*

LAI is a novel formulation of amikacin that is encapsulated in liposomes comprised of DPPC and cholesterol (naturally occurring lipids in the lung) to allow for effective delivery in the lung, leading to high concentrations of the drug at the target sites of infection, with low systemic levels. In clinical study TR02-112 LAI in addition to standard background therapy was statistically superior at the end of the double-blind period (Day 84) for achieving a negative sputum culture compared to those who received placebo in addition to standard background therapy.

Study INS-212 will evaluate whether there are any radiographical changes that occur in subjects who have achieved MAC culture conversion and continued on treatment.

### **Sub-Study Objectives**

1. To compare assessments of radiographs, read by a trained medical professional, from Baseline (Day 1) in CT scans at EOT in Japanese subjects from sites in Japan
2. To assess the safety of LAI by CT scans (at 6 month intervals) in subjects from sites in Japan

### **Sub-Study Design**

Eligible subjects must be enrolled into INS-212: A Randomized, Open-Label, Multicenter Study of Liposomal Amikacin for Inhalation (LAI) in Adult Patients with Nontuberculous Mycobacterial (NTM) Lung Infections Caused by *Mycobacterium avium* complex (MAC) That are Refractory to Treatment. The informed consent for this Japan specific CT Scan Sub-Study is included in the informed consent for the main study. All Japanese subjects in Japan will participate in this sub-study. There is no maximum number of subjects that can participate. The subject's Baseline chest CT scan must be collected no later than 2 weeks after the subject's first dose of LAI or multi-drug regimen in the INS-212 study. A prior chest CT scan may be used as a subject's Baseline measure if this CT scan was obtained within 6 months from the subject's Baseline (Day) 1 study visit in the INS-212 study. All subjects will have CT scans at their Months 6, 12, and EOT visits, and at 18 and 24 months after EOT.

Protocol Amendment #3 version: 22 February 2016

*This protocol is solely for the purpose of communicating information about the investigational drug between Insmid Incorporated and study personnel. Information is not to be reproduced, abstracted or used for sharing of information for any other purpose, whatsoever, except with the written permission of Insmid Incorporated.*

